
Coordinating Investigator Denmark [name] Sjællands Universitetshospital Næstved Klinisk Onkologisk Afdeling og Palliative Enheder [name] [contact] E-mail: [contact]

Coordinating Investigator in Germany [name]. [name] Christian-Albrechts-University Kiel/ University Hospital Schleswig-Holstein, Campus Kiel Department of Radiation Oncology [name] Phone: [name] E-Mail: [contact]

Co-Investigator in Lubeck, Germany [name]. [name] Department of Radiation Oncology, University of Lübeck & Department of Radiation Oncology, University Hospital Schleswig-Holstein [name], Germany [contact] Email: [contact]

Clinical Study Center KFE Sjællands Universitetshospital Næstved Klinisk Onkologisk Afdeling og Palliative Enheder [name] Phone: E-mail:

2 Synopsis

Study title	Palliative radiotherapy to dominant symptomatic lesion
Short title	PRADO
Study type	Multicenter feasibility study
Patient cohort	Patients with hormone refractory prostate cancer (HRPC) presenting a dominant symptomatic lesions
Sponsor	Sjællands Universitetshospital Næstved Klinisk Onkologisk Afdeling og Palliative Enheder
Primary Investigator	[name], Phd Sjællands Universitetshospital Næstved Klinisk Onkologisk Afdeling og Palliative Enheder
Objective	Feasibility and Safety of local hypo-fractionated radiotherapy of MR outlined lesion for the patient's dominant symptom.
Inclusion criteria (all criteria must be fulfilled)	
 • Patients with hormone refractory biopsy proven prostate cancer • Presenting with a dominating debilitating symptom • Expected median survival of 3 – 12 months • Focal irradiation of lesion is feasible • Systemic therapy according to guidelines • age ≥ 18 years • Legal capacity, patient is able to understand the nature, significance and consequences of the trial • Written informed consent
Exclusion criteria (recruitment is not possible if any -at least one- criterion is met)	
 • Relevant comorbidity (with limitations to administer radiotherapy according to protocol) • Prior radiotherapy which results in limitations to administer radiotherapy according to protocol • No large metal implants in vicinity of lesion • Department dose constraints for normal tissue can't be met • Large bony lesions with extensive osseous destruction • Patients symptoms do not correlate with MR findings
Study therapy	
 • Image guided radiotherapy (IGRT) with hypo-fractionated simultaneous integrated boost (IMRT) • GTV1 = MR T2w lesion and ADC $\leq 1200 * 10^{-3}$ mm2/s • GTV2 = MR T2w lesion and ADC \leq median ADC in GTV1 • Each lesion is a CTV, CTV = GTV • PTV=CTV+ margin according to department standards • Dose-fractionation • CTV1: 4 x 5 Gy • CTV2: 4 x 7 Gy
Primary endpoint	Feasibility: Proportion of study participants that complete radiotherapy with $\geq 90\%$ of prescribed dose
Secondary endpoints	
 • Dominant symptom (VAS) • Progression-free survival >6 months • Overall survival

	
• Acute toxicity• Quality of life• Change in ADC from before to end of treatment• Change in ADC from before to 6 month post treatment
Sample size	34 patients has to be included in the study
Study sites	University Hospital Sjaelland, Naestved UKSH Campus Kiel UKSH Campus Luebeck
Time table	Recruitment period: 12 months Start of study: March 2018 End of study: March 2019 Follow-up: minimum \geq 6 months
Financing	Interreg (InnoCan)

3 Background and rationale

Prostate cancer is the major cause of cancer death in men living in developed countries. Large autopsy studies found that patients that presented prostate cancer demonstrated metastatic disease in 35% of cases. Prostate cancer metastases were 90% bone metastases, with 90% of the bone metastases involved the spinal cord, followed by lung (46%), liver (25%) and pleura (21%). Another important pathway is the lymphatic system, which is involved in 9 to 16% of cases, especially at the level of obturator, pre-sacral, internal, and common iliac arteries, and sometimes even the extra-regional para-aortic chains (1).

Metastatic or locally advanced prostate cancer (PC) responds well initially to hormonal manipulation by androgen withdrawal and peripheral androgen blockade. However, such patients have high risk of progression to a hormone-refractory prostate cancer (HRPC). Once the tumor has achieved a castration-refractory metastatic stage, treatment options are limited and the average survival of patients ranging from two to three years only (2). Furthermore, HRPC patients will typically be frail old men.

Skeletal metastases account for most of the morbidity in surviving HRPC patients, but patients may also present with dominating disabling symptoms from local pelvic disease progression with an incidence estimated to be about 10%-18% (3, 4), or even higher in node-positive patients treated with anti-androgen therapy alone (5).

In patients with a reasonable expected median survival (6), pelvic radiotherapy (RT) may provide an effective palliation. Studies have demonstrated, radiotherapy contributes to relief of hematuria, pain and other pelvic symptoms, with acceptable toxicity in the majority of patients with HRPC (7-9).

A recent systematic literature search demonstrated good overall symptom response rates despite large variations in radiotherapy dose and fractionation (10), which consequently warrants new prospective studies in this field.

Radiotherapy, dependent on radiation dose-volume, however may lead to increase in radiation-induced toxicities (11). Both GI and GU toxicities do increase with dose and volume of respectively rectum and bladder irradiated (12) (13) (14). Technological advancements in radiotherapy such as image-guided radiotherapy (GRT), intensity modulated radiotherapy (IMRT / VMAT), stereotactic body radiation therapy (SBRT) or stereotactic radiosurgery (SRS) have allowed for significant treatment volume reduction, less normal tissue toxicity and whole-organ dose escalation. A recent review list several retrospective studies showing the effectiveness of SBRT and SRS in prostate cancer metastases (15)

Even further improvement may be obtained using more accurate imaging diagnostics for treatment planning, such as advanced MRI (16, 17). Using diffusion weighted imaging (DWI) quantitative measures such as the apparent diffusion coefficient (ADC) has been shown to be the most important imaging modality for predicting tumor location (18) (19) and local tumor recurrence larger than 0.4 ml (20).

The aim of the present study will be to conduct a feasibility study of a new short palliative radiotherapy regime that apply to patients with metastatic HRPC patients presenting with a dominating debilitating symptom and an expected reasonable survival. The dominant symptom can be such as pain, urinary retention, chronic rectal obstruction, bleeding etc., caused by localized progression of the patient's metastatic prostate cancer. This new approach will apply magnetic resonance imaging (MRI) to verify correspondence between the progressing HRPC lesion (DSL =the dominant symptomatic lesion) and the patients corresponding dominant symptom. Diffusion weighted MR imaging (DWI) will apply to identify both the lesion and the most aggressive part of the lesion. The symptomatic lesions will be treated using precision radiotherapy (IGRT+IMRT/VMAT or SBRT/SRS if available) with a dose of 4 x 5 Gy, while for the most aggressive part of the lesion the dose will be escalated to 4 x 7 Gy using a simultaneous integrated boost (SIB) technique.

4 Objective

This prospective study will evaluate the feasibility as the primary endpoint. Secondary endpoints are visual analog score (VAS) of the dominating symptom, symptom progression free survival, evaluation of radiation induced acute toxicity, the influence on quality of life, the progression free survival and change in volume and ADC statistics from baseline as surrogate marker of local response to radiotherapy. The study will analyze patient characteristics, relevant comorbidities and tumor related factors correlation to outcomes. Based on the results of this study, a prospective randomized phase II/III dose escalation study may suggested.

5 Study design and participating centers

This is an international, multi-center single arm prospective feasibility study. Participating sites are:

1. University Hospital Sjaelland, Naestved, Department of Oncology
2. UKSH Campus Kiel, Department of Radiation Oncology
3. UKSH Campus Luebeck, Department of Radiation Oncology

6 Inclusion and exclusion criteria

Patients can be included in the study if they fulfill all of the following inclusion criteria and none of the following exclusion criteria.

Inclusion criteria:

- Patients with hormone refractory biopsy proven prostate cancer (HRPC)
- Presenting with a dominating debilitating symptom
- Expected median survival of 3-12 months (6)
- Focal irradiation of lesion is feasible
- Systemic therapy according to guidelines
- age ≥ 18 years
- Legal capacity, patient is able to understand the nature, significance and consequences of the trial
- Written informed consent

Exclusion criteria:

- Relevant comorbidity (with limitations to administer radiotherapy according to protocol)
- Prior radiotherapy which results in limitations to administer radiotherapy according to protocol
- No large metal implants in vicinity of lesion
- Department dose constraints for normal tissue can't be met
- Large bony lesions with extensive osseous destruction (e.g. vertebral body)
- Patients symptoms do not correlate with MR findings

7 Risks and toxicities

Patients participating in this study will have standard radiotherapy. Consequently, the participating patients face known risks and toxicities following high dose radiotherapy. Patients participating in this study are offered a higher than normal radiation dose to their dominant lesion, but treatment plans will adhere to department standard dose constraints for all organs at risk in order to avoid excessive risks and toxicities.

8 Registration

The consecutive cohort of HRPC patients will be screened for eligibility according to the inclusion criteria's in this protocol. Estimated median survival for patients to be included should preferably be based on the updated model in (6) (see appendix 1). Before inclusion, patient clinical routine blood lab and radiology results should be reviewed. Available clinical routine diagnostic imaging and lab results may be used to calculate the expected median survival for patients using the model in (6) (see appendix 1). (6)Eligible patients will be informed about the study. After given informed consent, patients may be included in the

study. All patients included in the study receive a patient identification number (PID). The PID is composed of the site number and the running patient number (starting with P01, P02,.. ect.).

Site	SiteID
Naestved, Denmark	C1
Kiel, Germany	C2
Lübeck, Germany	C3

For **pseudonymous** registration and recording of all protocol data, the department of oncology, Naestved, will be make an electronic web interface (Easytrial) available for participating sites.

9 Systemic therapy

Systemic therapy will be administered according to department standard guidelines. Systemic therapy may be chemotherapy, anti-hormonal therapy, targeted therapies, bisphosphonates or a combination. The type of therapy will be documented. Interruptions of systemic therapy, delays or changes of drugs due to radiotherapy should be avoided.

10 Radiation therapy

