10.1 General remarks

The primary endpoint is feasibility. The secondary endpoints are duration of relief from local symptoms, i.e. local symptom progression free survival (LPFS), overall survival, treatment toxicity (RTOG/CTCAE 4.0), Quality of life (EORTC-QLQ-C30 and EPIC26), and change in ADC as surrogate marker of response (21-25). Patients are scheduled for protocol specific follow-up visits at 1, 3, 6 months after end of radiotherapy. Additional MRI (T2w and DWI) will be performed at 1 and 6 months after end of radiotherapy or in case of progression of the dominant symptom.

Preferred technique is hypo-fractionated with high precision radiotherapy (radiosurgery or stereotactic radiotherapy) with few (1 to 5) fractions and ablative total dose. Daily IGRT is mandatory for hypo-fractionated regimens. For the treatment of thoracic lesions and metastases in the upper abdomen, techniques for motion compensation (e.g. breath-hold- or gating techniques) should be used, if available. In specific situations (e.g. spinal metastases with involvement of the spinal canal or cord compression or metastases with infiltration of hollow organs), however, lower doses of radiotherapy may be necessary for adherence of dose constraints or to avoid radiation-induced complications such as perforation. In these cases, moderately hypo-fractionated or even conventionally fractionated regimens should be used. The total dose should exceed at least a dose equivalent to 50Gy in conventional fractionation.

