11.3 End of radiotherapy

At end of radiotherapy, the following must be documented:

- Review of concomitant medication, analgesia, opioids, current systemic anti-cancer treatment
- Review of clinical routine blood results and radiology
- Dominant symptom score (VAS score)
- Acute toxicity (NCI-CTCAE v4.03 score)
- Performance status (ECOG)
- Assessment of AE/SAEs

Details of actually applied treatment are to be documented throughout and to be entered into the CRF at the end of treatment:

- Radiotherapy techniques uses
- Volumes, fractions, doses applied, dose constraint compliance for all organs at risk
- Cumulative doses to target volumes, any boosts

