11.4 Follow-up visits

Protocol visits are required at registration for the trial and at end of radiotherapy and at 1,3 and 6 months after end of treatment (see flowchart in appendix 3). At this time, the following examination will be performed:

- Review of concomitant medication, analgesia, opioids, current systemic anti-cancer treatment
- Review of clinical routine blood and radiology results
- Dominant symptom score (VAS)
- Acute toxicities of radiotherapy , RTOG/NCI score
- Quality of life (EORTC-QLQ C30) (only at 6 months)
- ECOG performance status
- Assessment of AE/SAE

All later visits are scheduled according to standard guidelines and institutional procedures.

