11.5 Follow-up diagnostics

Protocol specific follow-up MR diagnostic scan is required for patient visit at one and six months after end of radiotherapy or at progression of the dominant symptom. The MR diagnostics should be performed according to the specifications in appendix 2. Remission status evaluated at 6 month based on available clinical data. Follow-up MR Scans will be co-registered to the baseline MR scan. Comparative volume and ADC statistics will be calculated as surrogate markers of response to radiotherapy.

12 Safety management

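### One of the two named ADC endpoints, change to end of treatment, has no MRI scheduled at that time point

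*Protocol*

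**What the plan says.** The secondary endpoints in the synopsis (section 2) include two ADC changes, listed separately: "Change in ADC from before to end of treatment" and "Change in ADC from before to 6 month post treatment".

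The scheduling text reads differently:

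- Section 10.1: "Additional MRI (T2w and DWI) will be performed at 1 and 6 months after end of radiotherapy or in case of progression". Progression here refers to the dominant symptom.
- Section 11.5: "Protocol specific follow-up MR diagnostic scan is required for patient visit at one and six months after end of radiotherapy". A scan when that symptom progresses is again the alternative.
- Section 11.3 opens with "At end of radiotherapy, the following must be documented". It then lists medication, routine blood results and radiology, VAS, toxicity, ECOG and adverse events. It orders no protocol MRI.
- Section 11.4: "Protocol visits are required at registration for the trial and at end of radiotherapy and at 1,3 and 6 months after end of treatment".
- Appendix 4 (flowchart): the MR scanning row is marked at baseline, 1 month and 6 months. The ADC Response row is marked after RT and at 6 months.

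Two passages describe the ADC comparison without a time point. Section 4 speaks of "change in volume and ADC statistics from baseline as surrogate marker of local response to radiotherapy", and section 11.5 says "Comparative volume and ADC statistics will be calculated as surrogate markers of response to radiotherapy".

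**The concern.** A change from baseline needs a measurement at both ends. For the first ADC endpoint the protocol provides the baseline scan and no scan at the stated end point.

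Scan acquisition is an instruction to sites, so an analysis plan cannot repair this later. With no end-of-treatment scan, the analyst can leave the endpoint empty or put the 1-month value in its place, and the protocol authorises neither. Sites may also diverge: one may add a scan to satisfy the flowchart's ADC tick after radiotherapy, while another follows the MR scanning row and does not. The early ADC data would then mix two time points.

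The early time point deserves a correct definition because patients are enrolled with an expected median survival of 3 to 12 months (section 6). The 6-month ADC endpoint will therefore lose patients to death, and the early one may be the better populated of the two.

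**Working it through.** The protocol gives no figure to reproduce here. The check sets the endpoint against every place that schedules MRI.

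**1. Does the endpoint need an MRI?** Yes. Section 10.3 calculates the ADC map from the DWI sequences.

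**2. Where are scans scheduled, and where is ADC response marked?**

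| Time point | MRI ordered in the text | MR scanning row | ADC Response row |
|---|---|---|---|
| Baseline | Yes (11.2) | marked | blank |
| End of radiotherapy | No (10.1, 11.3, 11.5) | blank | marked |
| 1 month | Yes (10.1, 11.5) | marked | blank |
| 3 months | No | blank | blank |
| 6 months | Yes (10.1, 11.5) | marked | marked |

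Only the 6-month endpoint has a scan at its own time point. The text of the synopsis and sections 10.1, 11.3 and 11.5 shows this without the flowchart.

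**3. Could end of treatment mean the 1-month visit?** No passage says so. Section 11.4 lists end of radiotherapy and 1 month as separate visits and counts the month from end of treatment. The flowchart gives them separate columns.

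**4. Could another scan fill the gap?** The progression scan occurs only in patients whose symptom progresses, and at no fixed time. The radiology item in section 11.3 reviews clinical routine results and orders no DWI.

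**5. Size.** With 34 patients (section 16.1) and all visits completed:

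- Scheduled MRIs: 3 × 34 = 102 at most.
- At end of treatment: 0 × 34 = 0.
- With an added end-of-treatment scan: 4 × 34 = 136, that is 136 − 102 = 34 more, and 34/102 = 33%.

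These are ceilings, since section 16.1 itself plans for 30% drop-out.

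**6. Illustration of why the early time point counts.** Assume exponential survival from the end of radiotherapy, S(t) = 0.5^(t/median), and 34 patients.

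| Median survival | Alive at 1 month | Alive at 6 months |
|---|---|---|
| 3 months | 0.5^(1/3) = 79% (about 27) | 0.5^(6/3) = 25% (about 9) |
| 12 months | 0.5^(1/12) = 94% (about 32) | 0.5^(6/12) = 71% (about 24) |

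The survival curve is my assumption; only the 3 to 12 month range is the protocol's.

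**7. A smaller mismatch of the same kind.** Section 10.1 names EPIC26 beside QLQ-C30 for quality of life. The visit lists in 11.2 and 11.4 name only QLQ-C30, and the flowchart row is generic. The main point does not depend on this.

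**The case against.** The strongest reply is that this is a wording slip with little consequence. The ADC change is a secondary, surrogate measure in a single-arm feasibility study, and no power calculation rests on it. The operational text is consistent: 10.1, 11.5 and the MR scanning row all give 1 and 6 months. Section 4 and section 10.1 fix no ADC time point, so the scheduled scans serve those general statements. A separate analysis plan might say that the first post-treatment scan is used.

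Much of this stands. The data loss is limited, and the scan counts measure workload rather than bias or precision. It is also fair that the documents do not show whether the label or the schedule is at fault. The flowchart tick after radiotherapy suggests that a measurement then may have been intended, and an ADC change just after four fractions is a different quantity from one a month later.

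The contradiction remains. The synopsis wording recurs in the flowchart, so it is not an isolated slip. An analysis plan could map the 1-month scan to the endpoint, but it would then be analysing something other than what the protocol names, and it cannot supply a scan that was never taken.

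**Conclusion.** The concern holds. The protocol contradicts itself: the synopsis and the flowchart's ADC Response row place an ADC assessment at end of treatment, while 10.1, 11.3, 11.5 and the MR scanning row schedule no scan there. One of two named ADC endpoints has no scheduled data.

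The damage is confined to that endpoint. The 1-month scan is acquired and falls under the general comparison with baseline in sections 4 and 11.5, but it has no named synopsis endpoint. The primary endpoint, sample size and safety rules are untouched. The finding rests on the text alone; the only assumption made, exponential survival, serves the illustration and not the conclusion. It should be corrected, though it does not threaten the trial's main result.

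**What to change.** Reconcile the synopsis, 10.1, 11.3, 11.5 and the Appendix 4 flowchart. The sponsor should state which time point was intended.

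- **If the 1-month scan is to serve:** restate the synopsis endpoint as the change in ADC from baseline to 1 month after treatment, and move the ADC Response tick from After RT to Visit 2. This takes edits in 2 places and no new scans. The cost is that the endpoint's time point shifts by one month, which should go through an amendment.
- **If a scan at end of treatment was intended:** add it to 10.1, 11.3, 11.5 and the MR scanning row. This takes edits in 4 places and one more MRI per patient, up to 34 in all, in a frail population.

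The first route is the cheaper and uses data already planned.

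In the same revision, settle whether EPIC26 is collected. If it is listed in 11.2 and 11.4 alongside QLQ-C30, and so given at baseline and 6 months, it adds up to 2 × 34 = 68 questionnaires. If it is removed from 10.1, the measurement of a secondary endpoint changes and that should be recorded as such.

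### The metal-implant exclusion criterion is worded in the reverse direction, identically, in the synopsis and in Section 6

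*Protocol*

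**What the plan says.** Section 6 of the Protocol gives the rule for combining the two lists: "Patients can be included in the study if they fulfill all of the following inclusion criteria and none of the following exclusion criteria". Its exclusion list then contains the item "No large metal implants in vicinity of lesion".

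The synopsis (Section 2) carries the same item, word for word, in its own exclusion list. The heading there states the rule even more explicitly: "recruitment is not possible if any -at least one- criterion is met".

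Two other items in the same lists are also phrased negatively: "Department dose constraints for normal tissue can't be met" and "Patients symptoms do not correlate with MR findings". The Protocol does not mention implants anywhere else, and it gives no reason for the criterion.

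**The concern.** The item is phrased as a condition that a suitable patient should satisfy, but it stands in a list where satisfying an item means exclusion. Taken at its word, the line turns away the patients the trial evidently wants and has no effect on those it was evidently meant to keep out.

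This matters because the line is part of the rule that decides who enters the trial. Section 8 has a consecutive cohort screened against the criteria. Section 5 names three sites in two countries, and Section 15 gives the German and Danish sites different monitoring arrangements. Eligibility should read the same way to everyone who applies or checks it. A checklist copied from the line without reading it for sense would have the wrong direction. A monitor who applied it literally would question the eligibility of patients who were properly enrolled.

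**Working it through.** No formula applies. The check is a logical reading of the list heading, the rule for applying the list, and the item itself, in each of the two places.

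**Step 1. State the item and the rule.** Let E stand for the item as written: the patient has no large metal implant near the lesion. Section 6 requires that patients "fulfill all of the following inclusion criteria and none of the following exclusion criteria", so entry requires that E is false. The synopsis heading leads to the same requirement.

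**Step 2. Apply the rule to both kinds of patient.**

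| Large metal implant near the lesion? | Is E met? | Result from this line alone, as written | Result if *No* is deleted |
|---|---|---|---|
| No | Yes | Excluded | Not excluded |
| Yes | No | Not excluded | Excluded |

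The outcome is reversed in both rows. A patient with only a small or distant implant belongs in the first row, because the item concerns large implants in the vicinity of the lesion.

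**Step 3. Check whether the list follows a different convention.** If the exclusion list were really a list of conditions to be satisfied, the implant item would be correct. The other negatively phrased items rule this out. In "Department dose constraints for normal tissue can't be met" the negated state is itself the reason to exclude, and the same is true of "Patients symptoms do not correlate with MR findings". Both work as exclusions. Among the negatively phrased items, only the implant line is reversed.

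**Step 4. Look for a correction elsewhere.** The synopsis and Section 6 use identical words, so neither can correct the other. There is no further text on implants in the treatment planning, target volume, baseline or MR sequence sections.

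**Step 5. Check for a numerical consequence.** Section 16.1 obtains 24 cases from a reference proportion of 90%, an alternative of 70%, 5% two-sided significance and 80% power. It then raises the number to 34 for an assumed 30% drop-out. The implant criterion is not an input to any of these figures, so none changes.

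**The case against.** The strongest reply is that nobody would be misled. The trial defines its targets on MR images and co-registers them to the planning CT, so a rule demanding a large metal implant beside the lesion makes no sense. Investigators would read the line for its intent. That stands, and it is the main reason for the low severity.

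A second reply is that the line is not the only safeguard. An implant that really prevented protocol treatment could fall under the inclusion item requiring that the lesion can be irradiated focally. It could also fall under the dose-constraint exclusion, or under the exclusion for symptoms that do not correspond to the MR findings. That also stands. A reader might infer that the Protocol leaves no ground at all for declining a patient with an implant. The documents do not support this: all the other criteria still apply, and only the implant line itself fails to exclude.

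A third reply concerns what is not shown. A reader might infer that the Easytrial entry form carries the same error. Section 8 says only that a web interface will be made available for registration and recording of data; no eligibility form appears in the Protocol. A reader might also take image distortion near metal as the stated purpose of the criterion. That is a plausible assumption, but the Protocol does not say it.

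None of these replies makes the wording correct. They limit its practical effect.

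**Conclusion.** The criterion is wrong as written, in both places, and nothing else in the Protocol corrects it. Severity is low. It is a mismatch between one item and its list heading, not a design decision.

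The literal reach is wide, since it covers every candidate without a large metal implant near the lesion. The expected practical effect is small, because the intent is easy to guess. A reader might infer that nearly all of the 34 planned patients would become protocol deviations. That assumes the line is applied with no reading for sense, which nothing in the documents shows. The Protocol also does not say how many candidates have such implants, so no count of affected patients can be given. Sample size, power and error rate are unaffected.

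The finding of reversal rests only on the wording of the item and of the two rules for applying the lists. The statement that it is a slip is an inference from the trial's reliance on MR-defined targets and from the direction of the neighbouring items.

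**What to change.** Reconcile the line with its list heading in the synopsis and in Section 6. Either of two edits does this:

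- delete the word *No* and leave the line among the exclusion criteria; or
- move the line unchanged to the inclusion criteria.

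The two are logically equivalent, and the same choice should be made in both places. The sponsor should also check that any eligibility form or screening checklist based on the line has the intended direction, and correct it if it does not.

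The cost is one word, or one relocated line, in two places, plus that check. No statistical section needs to change.
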